9.7. Data Analysis

The Statistical Analysis Plan (SAP) for this study will be outlined in this section, not in a separate document. Consequently any major modifications to the analysis plan will be reflected in a NI protocol amendment. Statistical Analysis Software (SAS) (Version 9.1, 9.2, 9.3 or 9.4) will be used for all analyses.

Descriptive Analysis

Descriptive statistics will be reported for all variables of interest. Results will be reported in aggregate, and for the subgroups described below provided there are sufficient subjects in each subgroup to create a meaningful summary. The number and percent of patients along with descriptive statistics (mean, standard deviation, median, 25th and 75th percentiles, number of non-missing and number of missing values) will be reported for continuous data. Categorical variables (eg, age groups) – sometimes created from continuous variables – will have the number and percent of patients reported. In case of missing observations, the calculation of percentages will always include the missing category. Counts of missing observations will thus be included in the denominator and presented as a separate category. Patient demographics, selected clinical characteristics, and line of therapy treatment response will be summarised.

Baseline characteristics

All baseline characteristics will be summarised by the treatment groups listed below, where the data are available:

- Gender (male/female);
- Race (Caucasian, Other);
- Age;
 - Continuous variable;
 - Categorical: <65, 65-74, 75-84, and ≥ 85 ;
- Weight (kg);
- Height (m);
- BMI (Weight[kg]/Height[m]²);
- Co-morbidities;
- Risk Stratification: IMDC (Heng) and/or MSKCC;

- Date of metastatic and/or advanced RCC diagnosis (dd/mm/yyyy);
- RCC diagnosis (advanced or metastatic);
- Stage at diagnosis (eg, TNM).

Treatment groups

The proposed analyses will be presented for each of the following treatment groups:

- Sunitinib as a first line therapy;
- Axitinib as a second line therapy eg, post-sunitinib, post-pazopanib etc.

Descriptive analyses will be presented for each of the following treatment groups:

- Axitinib as a third line therapy;
- Axitinib (and, if applicable, sunitinib) post-immunotherapy (IO), taking into consideration 2nd and 3rd therapy lines, following all IO therapy options.
 - eg, atezolizumab/bevacizumab, nivolumab/ipilumimab, nivolumab, interleukin-2.

Primary Endpoint

Progression free survival (PFS)

PFS will be measured from the index date of each treatment line to the date of progression, or date of death due to any cause, or date of initiation of new regimen. Patients who are still alive and have not progressed at the last office visit date without clinical or radiographic evidence of progression will be censored (final study cutoff will be June 2017). PFS will be estimated in months using the Kaplan-Meier method with 95% CIs, and summary tables of the number of events and censored patients at each month interval included. Kaplan-Meier plots for PFS will be presented for the overall population and stratified by MSKCC/IMDC risk category (favourable, intermediate, poor). A log rank test will be performed to compare the stratification groups.

Secondary Endpoints

All secondary endpoints will be analysed as follows:

Overall survival (OS)

OS will be defined as the time between the index date (dependent on treatment line) and the date of death from any cause. Patients who are still alive at the study end date or the last visit date available will be censored (using whichever occurred first). If a death date is known beyond the study end date, then the study end date (June 2017) will be used as the censoring

date. Median OS will be estimated in months using the Kaplan-Meier method with 95% confidence intervals (CIs), and summary tables of the number of events and censored patients at each month interval included. Kaplan-Meier plots will be presented for Overall Survival for the overall population, and stratified by MSKCC/IMDC risk (favourable, intermediate, poor). A log rank test will be performed to compare the stratification groups.

Best overall response (BOR)

In prospective clinical trials, BOR is generally assessed according to the Response Evaluation Criteria In Solid Tumours (RECIST) 1.1.¹³ However, the parameters underlying these criteria are less reliably available in retrospective, observational studies. While an attempt will be made to mimic the RECIST guideline, it should be noted that assessments based on information garnered during routine clinical practice could be more subjective than assessments in a controlled clinical trial and decision making about continued therapy could include symptomatic criteria. Additionally, timing of repeat imaging may vary. All evaluation in this observational study will be as best determined by clinicians, either as noted in the patient chart by the radiologist-written scan report or the treating physician's progress notes or as interpreted by the clinician reviewer. The BOR for a line of treatment is the best response across all timepoints during that line of therapy assessed using the following categories: Complete response (CR), Partial Response (PR), Stable Disease (SD), Progressive Disease (PD), Not Evaluable (NE).

Objective response rate (ORR)

BOR will be summarized as ORR, which is defined as the number of patients having reached a BOR of CR or PR divided by the number of patients (the primary analysis population), including the NE patients.

ORR = Number of patients achieving a response (BOR = PR or CR)/Number of patients (BOR=CR+PR+SD+PD+NE).

Patients who do not have a BOR assessment for a particular line of therapy will be excluded from the summary for that line of therapy. The number of patients with a missing BOR assessment will be summarized.

Duration of response (DOR)

DOR will be calculated for each patient with a BOR of CR or PR as the duration of time from first documented CR/PR, to the earliest date of first progression or recurrent disease, or date of death, or date of initiation of new regimen. Patients who are still alive and did not progress will be censored at the last physician office visit date without clinical or radiographic evidence of progression. DOR will be estimated in months using Kaplan-Meier method with 95% CIs, and summary tables of the number of events and censored patients at each month interval included.

Time to treatment discontinuation (TTD)

TTD will be calculated as the duration between the start of a treatment line to the end of the treatment line for patients with discontinuation of treatment for any reason, or censoring if a stop date is not documented (at end of study), if the patient dies, is lost-to follow up, or is still on-therapy. Patients without a discontinuation event will be censored on the study end date or at last office visit date without clinical or radiographic evidence of progression, whichever occurred first. Time to TTD will be analysed using the Kaplan-Meier method with 95% CIs, and summary tables of the number of events and censored patients at each month interval included.

Durable response rate (DRR)

DRR will be determined as the proportion of patients with objective response (CR or PR) with a duration of at least 6 months. Duration of response will be calculated as previously defined for DOR.

Time-to-Event Analysis

The Kaplan-Meier method will be used to estimate median OS, PFS and TTD. P values comparing survival curves by stratification groups, will be calculated using log-rank tests. Univariate and multivariable Cox proportional hazards regressions will be used to evaluate explanatory factors and to calculate hazard ratios (HRs) with two-sided 95% CIs for OS, PFS and TTD. Demographic and clinical factors will be included in multivariable Cox regression models based on their clinical relevance and/or the univariate significance level (assessed at the level of $p < 0.05$).

In order to account for the impact of baseline patient and disease characteristics outlined in this protocol and the disease characteristics below, unadjusted Cox models and multivariable Cox models adjusting for selected patient demographics and clinical characteristics identified by Pfizer as clinically relevant will be included in the adjusted models. Time-to-event analyses will be assessed in the overall population and by stratifications of interest (MSKCC/IMDC category). The disease characteristics of interest are:

- a. Less than one year from time of diagnosis;
- b. Karnovsky performance status less than 80%;
- c. Haemoglobin less than the lower limit of normal (eg, less than 12 g/dl);
- d. Serum calcium greater than the upper limit of normal (eg, 10 mg/dl or: 2.5 mmol/l);
- e. Neutrophil greater than the upper limit of normal (eg, greater than 7.0×10^9 dl);
- f. Platelets greater than the upper limit of normal (eg, greater than 400 000);
- g. Lactate dehydrogenase greater than 1.5 times the upper limit of normal;

- h. Fuhrmann grade of tumour;
- i. Tumour subtype eg, clear cell vs. non-clear cell.

The SAP outlined in this section may be subject to modifications; any major modifications of primary endpoint definitions or their analyses would be reflected in a protocol amendment.

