6. MILESTONES

Milestone	Planned date
Start of data collection	01 August 2019
End of data collection	15 August 2019
Final study report	31 October 2019

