9.2. Setting

All data will be sourced retrospectively from participant medical records of care received at The Christie NHS Foundation Trust.

NHS staff members with permitted access to medical records have searched the electronic medical record database and paper medical records to identify participants. This data collection was conducted independently of this study, at an earlier time point. This is a clinical database, used in the routine care of patients.

Patients with a diagnosis of renal cell carcinoma will be eligible for inclusion, and recruitment of patients to the wider data collection study at the NHS trust is/was by consecutive ongoing enrollment. This cohort is therefore felt to be representative of the patient population being studied.

Patients were followed up until they withdrew consent, death occurred or the patient could no longer be contacted by the clinical team. Data collection for the wider study is ongoing.

For this non-interventional study, patients who have been treated with sunitinib and/or axitinib will be selected, as these are the medicines of interest to the Pfizer Oncology team.

This is a secondary data collection study, as the clinical database already exists, and the clinical academic team who administrate the database have agreed to provide data to the Pfizer team for research purposes.

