9.2.1. Inclusion Criteria

1. Over the age of 18 years.
2. Diagnosis of renal cell carcinoma.

3. Treatment with sunitinib and/or axitinib.
4. Timeframe: from database inception date (2002) until the end of June 2017.

Research Ethics Committee (REC) approval has been sought in the UK. The Integrated Research Application System (IRAS) number for this study is: 266899 and the REC number is 19/LÖ/1041. No data will be transferred until this approval has been granted.

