9.3. Variables

Variable	Operational definition
Demographic details	Anonymised, linked details
Diagnosis Date	Date of diagnosis
Diagnosis	Renal cell carcinoma: clear cell, non-clear cell
Prior surgery eg, nephrectomy	Yes/No; add details as necessary
Line of therapy	1 st line, 2 nd line, 3 rd line
Start date	Start date of therapy
Drug treatment	Drug name
MSKCC Risk Grade	Numeric value, subcategorise if possible: favourable/intermediate/poor risk. Include individual parameters that comprise this grading system where possible
IMDC/Heng Risk Grade	Numeric value, subcategorise if possible: favourable/intermediate/poor risk. Include individual parameters that comprise this grading system where possible
ECOG performance status at outset	Numeric value with related functional level attributed to this
TNM Stage	3 part cancer staging system; provide details where possible
Histology; Fuhrmann grade	Histopathological diagnosis and grading system
Metastasis diagnosis, if applicable	Site and extent of metastatic disease
Response to treatment	PFS, OS, TTD, Best overall response (BOR)
Date of discontinuation	Date of discontinuation of drug treatment
Therapy discontinuation	Reason for discontinuation

Data cut offs	Overall survival, loss to follow-up, withdrawal from study Data cut-off date for OS and PFS is June 2017
Adverse event reporting	It is expected that this data will have been reported through normal mechanisms, and will not have been recorded in the clinical database

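### The OS rules credit survival time after the last visit only to patients whose death is recorded, so OS is biased low when such deaths are captured; the size cannot be fixed from the documents

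*Combined protocol and SAP*

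**What the plan says.** Section 9.7 defines the endpoint: "OS will be defined as the time between the index date (dependent on treatment line) and the date of death from any cause". Three endings follow.

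1. Death known on or before the study end: an event at the date of death.
2. Death known after the study end: censored at the study end, whatever the last visit date ("If a death date is known beyond the study end date, then the study end date (June 2017) will be used").
3. No known death: "Patients who are still alive at the study end date or the last visit date available will be censored (using whichever occurred first").

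Section 9.3 fixes the cut-off: "Data cut-off date for OS and PFS is June 2017". Section 9.2 describes how follow-up could end: "Patients were followed up until they withdrew consent, death occurred or the patient could no longer be contacted by the clinical team". It adds "Data collection for the wider study is ongoing". Section 6 puts the end of data collection for this study at "15 August 2019", about 26 months after the cut-off.

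The documents do not say how deaths are ascertained, whether vital status is traced after contact is lost, how often patients are seen, or whether visits after June 2017 are in the extract. No sensitivity analysis of OS censoring is planned.

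**The concern.** Kaplan-Meier, log-rank and Cox analyses all need censoring that is unrelated to the later outcome. Take three patients last seen in January 2015. One dies in 2016 and is an event in 2016. One dies in 2018, the death becomes known, and the patient stays at risk until June 2017. One has no recorded death and leaves the risk set in January 2015. The second and third were both alive in June 2017, yet the second contributes about 29 more months, only because a death was recorded later.

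Once a patient's own last visit has passed, that patient stays in the risk set only if a death is on record. Deaths in that stretch are counted without the matching time of those who survived it, which inflates the hazard. OS, overall and by risk group, is the first secondary objective in both lines (Section 8), and a larger sample would not remove the bias.

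**Working it through.** The plan gives no OS figure to reproduce. The check covers direction, size, and the part played by each rule.

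**Direction.** Consider only time between last visit and June 2017. Let D be the deaths in it, P_D the person-time of those who die before June 2017, and P_A the person-time of those alive at June 2017. Let p be the share of those deaths that is known, and q the share of P_A that is counted because a later death is known.

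- True hazard: D / (P_D + P_A).
- Hazard under the plan: pD / (pP_D + qP_A).
- The second exceeds the first if and only if p(P_D + P_A) > pP_D + qP_A, that is, p > q.

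If deaths are captured equally well before and after June 2017, q = p × F, where F is the probability of dying in the 26-month look-ahead. With exponential survival and median m, F = 1 − 2^(−26/m).

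| Median m (assumed) | F | Survivor time omitted if p = 1 (1 − F) |
|---|---|---|
| 40 months | 0.36 | 0.64 |
| 20 months | 0.59 | 0.41 |
| 8 months | 0.90 | 0.10 |

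F is below 1, so q < p and OS reads low, with most survivor time omitted where survival is longest.

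**Size.** Kaplan-Meier medians were simulated under the Section 9.7 rules, 400,000 exponential survival times per cell, uniform entry. From the documents: the three rules, the June 2017 cut-off and the 26-month look-ahead. Assumed: true medians of 40, 20 and 8 months, the entry period (Section 9.2.1 gives only 2002 to June 2017, not entry by drug), 3-month visits, the share lost, and the capture of deaths after loss. Percentages come from unrounded medians; differences under about 0.5% are simulation noise.

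| Entry (months) | Visits after cut-off in extract | Lost | Deaths after loss captured | True 40 | True 20 | True 8 |
|---|---|---|---|---|---|---|
| 60 | no | 0% | – | 39.0 (−2.6%) | 19.8 | 8.0 |
| 60 | no | 20% | all | 36.9 (−7.7%) | 19.4 | 8.0 |
| 60 | no | 20% | none | 38.8 (−3.1%) | 19.6 | 7.9 |
| 60 | no | 40% | all | 35.1 (−12.4%) | 19.1 | 7.9 |
| 60 | yes | 20% | all | 38.0 (−5.0%) | 19.7 | 8.0 |
| 138 | no | 20% | all | 38.9 (−2.8%) | 19.8 | 8.0 |
| 138 | no | 20% | none | 39.4 (−1.6%) | 19.8 | 7.9 |
| 138 | yes | 0% | – | 39.9 (−0.2%) | 20.0 | 8.0 |

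A second set assumed 60- or 132-month entry, visits every 3 or 6 months, 0–20% per year leaving contact with all deaths still captured, and a 25-month look-ahead. Over repeated runs, a true median of 48 read 37.4–47.7, a true 24 read 21.9–23.9, and a true 15 read 14.5–15.0. The low end for 48 is (48 − 37.4)/48 = 22%. It needs 60-month entry, 6-month visits, 20% yearly loss and full death capture together. With 132-month entry and 0–5% yearly loss, 48 read 45.4–47.7, or 0.6% to 5.4% low.

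**Which rule does it.** In that worst cell the median is 37.4 with the sentence on deaths beyond the study end and 33.7 without it. The sentence returns some survivor time.

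**Alternatives.** With full tracing, censoring everyone without a death by the cut-off at the cut-off recovers the truth (47.8–48.2 for 48; 40.0/20.0/8.0 for 40/20/8). If deaths after loss are missed, it overshoots: 43.6 for 40 (138-month entry, 20% lost), and about 56 for 48 at 5% yearly loss, which is 8/48 = 17% high. A common horizon for deaths and survivors gave about 40.0/20.0/8.0 whether or not deaths after loss were traced.

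**The case against.** The strongest objection is that the large figures rest on something the documents never state: that patients leave contact while their deaths are still recorded. Section 9.2 says follow-up stopped when contact was lost. If later deaths are not captured, last-visit censoring is close to right (47.2 for a true 48 with 5% yearly loss, 3-month visits and 132-month entry). If visits after June 2017 are in the extract, attending patients are censored at June 2017, and with no loss the bias vanishes. OS is also secondary, in a study described as descriptive.

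This limits the size but does not remove the fault. With later visits in the extract and 10–20% yearly loss with deaths captured, a true 48 still reads 39.0–44.6. The only simulated cells not biased low (about 0 to +1%) assumed that deaths of lost patients are never known before June 2017 but always known after it.

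Three stronger readings are tempting and not supported.

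- A reader might blame the sentence on deaths beyond the study end. It is ordinary administrative censoring and reduces the bias.
- A reader might infer from it that such deaths are on file. It is conditional: it provides for them without showing that they exist.
- A reader might conclude that the log-rank tests and hazard ratios between risk groups are materially distorted. Neither was computed. The loss in months is largest in long survivors, but relative losses can be similar or even reversed: −2.1%, −2.4% and −3.1% for medians of 40, 20 and 8 with 60-month entry, later visits in the extract, 40% lost and no deaths captured after loss.

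**Conclusion.** The point holds as a fault in the stated rules: follow-up after the last visit depends on later outcome, and OS is biased low when deaths after the last visit are captured. The direction is firm if deaths are captured equally well before and after June 2017. The size is not: it depends on entry period, visit interval, loss, death capture and true survival, none of which the documents give. It runs from near zero to about a fifth of a 48-month median, and the upper end is an extreme combination rather than an expected value. Loss of sicker patients is a separate bias that could push OS up under any of these rules. The point does not concern the primary PFS analysis. It warrants a change before the OS analysis because the correction is cheap and the size cannot be judged in advance.

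**What to change.** Use one follow-up horizon for deaths and survivors alike, and state in Section 9.7 how deaths are ascertained and to what date.

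1. If vital status is ascertained to 30 June 2017 for all patients, censor everyone without a death by that date at 30 June 2017, regardless of last visit.
2. If it is not, end each patient's follow-up at a last-contact horizon that does not depend on outcome, for example last visit plus a fixed window, capped at 30 June 2017. Count only deaths inside it as events and censor all others at its end, including patients whose death is known later. The window should be no shorter than the usual visit interval; otherwise deaths between visits are dropped and OS reads high. Deaths inside it must be reliably known.

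Falling back on the last date known alive would not be enough, because it stays asymmetric if deaths are traced and survivors are not. Report the present rule as a sensitivity analysis, without claiming that the two results bound the truth.

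The cost is a wording change and one more OS run. Rule 1 overstates OS materially if deaths after loss are missed, so it should be used only with complete tracing. Rule 2 discards some known deaths and loses a little precision.

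### Best overall response has no cut-off at first progression, so a first CR/PR recorded after PD counts as a response and conflicts with PFS and DOR

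*Combined protocol and SAP*

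**What the plan says.** All the relevant definitions are in Section 9.7, which states that there is no separate SAP document.

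- **BOR:** "The BOR for a line of treatment is the best response across all timepoints during that line of therapy". The paragraph opens with a hedge, "While an attempt will be made to mimic the RECIST guideline", and warns that in routine practice "decision making about continued therapy could include symptomatic criteria".
- **ORR:** "the number of patients having reached a BOR of CR or PR divided by the number of patients", with not-evaluable patients kept in the denominator and patients without any BOR assessment left out.
- **DOR:** for every patient whose BOR is CR or PR, the "duration of time from first documented CR/PR, to the earliest date of first progression or recurrent disease", or to death or a new regimen if sooner. Nothing requires the progression to come after the response.
- **DRR:** objective response lasting at least 6 months, using the DOR definition.
- **PFS (primary):** "PFS will be measured from the index date of each treatment line to the date of progression, or date of death due to any cause". Starting a new regimen also counts as an event.
- **Line of treatment, as used for TTD:** "the start of a treatment line to the end of the treatment line for patients with discontinuation of treatment for any reason". Progression does not in itself end the line.

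The variable table in Section 9.3 lists PFS, OS, TTD and BOR under response to treatment. It lists no date of first response.

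**The concern.** BOR and PFS are measured over different windows. The PFS clock stops at the first progression. The BOR window stays open until the drug is stopped. Any assessment made between a recorded PD and discontinuation therefore lies inside the BOR window but after the PFS event.

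Only one sequence causes trouble: a first CR or PR recorded after a first PD in the same line. The plan's wording allows this to arise. Response may be taken from the scan report, the progress notes or the reviewer's interpretation, with no order of precedence among them, and progression may be clinical or radiographic. A clinical progression in the notes followed by a scan read as PR would fit these definitions.

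ORR and DOR are secondary objectives for both lines, and DRR is derived from DOR. For a patient with this sequence, ORR disagrees with PFS, and the programmer has to choose between two unsatisfactory versions of DOR without guidance from the plan.

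**Working it through.** The plan gives no ORR, no rate of treatment past progression and no power calculation, so there is no figure of its own to reproduce. The check has two parts.

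**1. Applying the definitions to two illustrative patients** (months from index; all dates assumed)

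Formulas:
- PFS = min(progression, death, new regimen) − index.
- DOR, literal = min(first progression in the line, death, new regimen) − first CR/PR.
- DOR, alternative = min(first progression after the response, death, new regimen) − first CR/PR.

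| | Patient A | Patient B |
|---|---|---|
| Sequence | PR at 3, PD at 9, new regimen at 10 | PD at 3, first PR at 6 on the same drug, second PD at 12, new regimen at 12.5 |
| PFS | event at 9 | event at 3 |
| BOR as written | PR | PR |
| In ORR numerator | yes | yes |
| DOR, literal | 9 − 3 = +6 | 3 − 6 = −3 |
| DOR, alternative | 9 − 3 = +6 | 12 − 6 = +6 |
| Durable (at least 6 months) | yes | no valid value, or yes |

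Patient A shows that PR followed by PD causes no conflict. Patient B fails on either reading. The literal one gives a negative time, which a Kaplan-Meier analysis cannot use. The alternative gives a durable responder whose response began three months after the PFS event.

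**2. Size of the effect on ORR**

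Inputs: a share a = 20-30% of patients treated past first progression, and a share b = 5-10% of those with a later first PR. Both are assumptions; the documents give neither. Cohort totals of 678 (sunitinib) and 163 (axitinib) are from Section 9.5.

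- Rise in ORR, q = a × b: 0.20 × 0.05 = 1.0 point; 0.30 × 0.10 = 3.0 points.
- Sunitinib: 678 × 0.01 = 6.8 and 678 × 0.03 = 20.3, so about 7 to 20 patients.
- Axitinib: 163 × 0.01 = 1.6 and 163 × 0.03 = 4.9, so about 2 to 5 patients.
- Share of counted responders with PD before response, at an assumed ORR of 20% before these cases are added: 0.01/0.21 = 4.8% to 0.03/0.23 = 13.0%.
- The same at an assumed 30%: 0.01/0.31 = 3.2% to 0.03/0.33 = 9.1%.

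At these rates the patient counts are upper bounds. The totals cover everyone who received each drug, not first-line sunitinib and second-line axitinib, and patients without a BOR assessment are excluded from ORR.

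**The case against.** The best defence is that the plan is silent on assessments after progression and does not expressly include them, and that the stated aim of following RECIST points to a conventional BOR. This shows intent, but the plan only promises an attempt, sets no rule for readings after PD, and then states its own operative definition. That definition is what would be programmed.

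Second, an end event paired with recurrent disease is most naturally read as following the response, so DOR would not be negative. This is a fair reading. It removes the impossible value but leaves the disagreement with PFS, and patient B then counts towards DRR.

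Third, Section 7 describes best response as an item already collated, and Section 9.3 lists no serial assessments, so the window may be hard to shorten. This affects the effort but does not defeat the change. DOR cannot be calculated without the date of first response, nor PFS without the date of progression. Those two dates are enough to decide whether a patient counts as a responder.

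Three stronger readings are tempting but not supported:

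- *Treatment past progression is expected.* The remark on symptomatic criteria is a caveat about subjectivity. Symptoms could equally lead to stopping before a radiographic PD. No section says how often treatment continued past progression, and it could be close to never.
- *DOR will be negative in general.* It is negative only when the first response follows the first PD and first progression is also taken literally.
- *Being both progressed and a responder is itself an error.* Any patient with PR and later PD is both; only the reverse order conflicts.

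The plan also does not say how a negative duration would be handled, so no particular treatment of such records should be presumed.

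**Conclusion.** The point holds for one sequence, a first CR or PR recorded after a first PD in the same line. As written, the BOR rule classifies that patient as a responder although PFS has already recorded the failure. DOR is then either negative or, together with DRR, can credit a durable response that began after the PFS event. This is a rule that misclassifies patients, not merely missing detail.

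The number of patients affected cannot be determined from the documents and may be small. The rise of 1 to 3 points in ORR rests entirely on the assumed rates. The primary PFS analysis is unaffected. The change should be made before data transfer, because it also determines which dates are requested.

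**What to change.** In Section 9.7:

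- Define BOR as the best response from the index date up to the earliest of first progression, start of a new regimen, death or data cut-off.
- State that a first CR or PR dated after first progression does not count for BOR, ORR, DOR or DRR, and report such cases as a separate count for each line.
- State that the DOR end event is the first qualifying event after the response.

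In Section 9.3, add the date of first CR/PR to the data request, and confirm that the progression date behind PFS is supplied with it.

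The cost is modest. ORR becomes slightly less favourable, and some records may need a date query to the site. Where only a single best response is held, assigning a reclassified patient to SD or PD may need a look at the chart, but ORR, DOR and DRR need only the two dates.

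### Patients with no recorded best overall response are dropped from the ORR, against the plan's own rule that percentages keep missing values in the denominator

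*Combined protocol and SAP*

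**What the plan says.** Section 9.7 holds the whole analysis plan and treats missing data in two places.

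- **Descriptive Analysis.** The general rule is "In case of missing observations, the calculation of percentages will always include the missing category", followed by "Counts of missing observations will thus be included in the denominator and presented as a separate category". The same paragraph ends: "Patient demographics, selected clinical characteristics, and line of therapy treatment response will be summarised".
- **Secondary Endpoints, ORR.** This part is introduced by "All secondary endpoints will be analysed as follows". In words, ORR is the number with CR or PR "divided by the number of patients (the primary analysis population), including the NE patients". The formula's denominator is the sum of CR, PR, SD, PD and NE, with no term for missing. Then: "Patients who do not have a BOR assessment for a particular line of therapy will be excluded from the summary" for that line. Finally: "The number of patients with a missing BOR assessment will be summarized".

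Neither place refers to the other. The text supplied does not define the primary analysis population and gives no criterion for coding a patient as NE rather than leaving BOR missing.

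**The concern.** BOR is a categorical treatment response by line, and ORR is a percentage of it. The general rule therefore appears to cover it, yet the ORR rule does the opposite without saying that it is an exception. The ORR text also sits uneasily with itself. If the primary analysis population means everyone who started the line, the exclusion sentence then removes some of those patients from it.

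The boundary between NE and missing makes this worse. A patient who stopped or died before any usable scan could be coded NE, and so counted as a non-responder, or left blank, and so dropped. The ORR would then depend on coding habit in a routine clinical database. Section 9.7 itself warns, under BOR, that response information is less reliable in retrospective data, and section 9.6 expects some items to stay missing after chart queries.

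ORR is a secondary objective for both first-line sunitinib and second-line axitinib (section 8). What is at stake is whether the headline rate describes all treated patients or only those with a recorded response category.

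**Working it through.** The plan states no expected ORR, no missing-BOR share and no power calculation, so there is no figure of its own to reproduce.

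**Inputs**

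- Expected patients, section 9.5: 678 received sunitinib and 163 received axitinib. These counts are not split by line, so they are upper limits for the first-line and second-line groups.
- m, the share of patients starting the line with no BOR recorded: an assumption, shown from 1% to 20%.
- ORR among all who started the line: an assumption of about 30%, with a range of 10% to 40%.

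**Step 1: ratio of the two rates.** With R responders among N patients who started the line, the general rule gives R/N and the ORR rule gives R/(N(1 − m)). The ratio is 1/(1 − m), whatever R and N are: 1.010, 1.020, 1.053, 1.111 and 1.250 for m = 1%, 2%, 5%, 10% and 20%.

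**Step 2: percentage points at about 30%.** The all-started rate is 203/678 = 29.9% for sunitinib and 49/163 = 30.1% for axitinib. Dropping the patients with no BOR gives:

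| m | Sunitinib | Axitinib |
|---|---|---|
| 2% | 203/664 = 30.6% | 49/160 = 30.6% |
| 5% | 203/644 = 31.5% | 49/155 = 31.6% |
| 10% | 203/610 = 33.3% | 49/147 = 33.3% |
| 20% | 203/542 = 37.5% | 49/130 = 37.7% |

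Before rounding, the gap for sunitinib is 0.6, 1.6, 3.3 and 7.5 points.

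**Step 3: comparison with sampling error.** The Clopper-Pearson 95% intervals for the all-started rate are 26.5–33.5% (203/678) and 23.1–37.7% (49/163). The table gives the smallest number dropped, k, for which x/(N − k) exceeds the upper limit, where x is the number of responders:

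| Assumed ORR | N = 678: x, k | N = 163: x, k |
|---|---|---|
| 10% | 68, 136 (20.1%) | 16, 60 (36.8%) |
| 20% | 136, 94 (13.9%) | 33, 42 (25.8%) |
| 30% | 203, 73 (10.8%) | 49, 34 (20.9%) |
| 40% | 271, 59 (8.7%) | 65, 28 (17.2%) |

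Smaller line groups have wider intervals and so higher thresholds.

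**Step 4: which rate is nearer the truth.** Let r be the response rate of patients without a BOR relative to those with one. Then recorded-BOR rate / truth = 1/(1 − m(1 − r)), and all-started rate / truth = (1 − m)/(1 − m(1 − r)). At m = 10%:

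| r | Recorded-BOR / truth | All-started / truth |
|---|---|---|
| 0 | 1.111 | 1.000 |
| 0.5 | 1.053 | 0.947 |
| 1 | 1.000 | 0.900 |

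For any r between 0 and 1 the two rates bracket the true one.

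**The case against.** The strongest reply is that a specific rule overrides a general one. The rule on missing values sits under Descriptive Analysis, next to an example about age groups, and can be read as governing frequency tables. ORR has its own formula, its own exclusion sentence and its own line on the missing count. The two can even coexist: a BOR table with a missing row, and an ORR computed as a separate ratio. This largely stands as a prediction of what an analyst would do. It does not supply the unwritten exception to a rule worded as holding always, and it leaves open who is in the population and how NE differs from missing.

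Second, the size is unknown. Best response is listed in section 7 as already collated, section 9.6 provides chart queries for missing data, and if patients without a usable scan are coded NE then m could be close to zero. This stands, and no claim is made that m is large.

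Third, bias is not demonstrated. The recorded-BOR rate overstates the truth only if unassessed patients respond less often, which is plausible but not shown. Counting every blank as a non-response can err the other way. This also stands, and is the reason to report both rates.

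Fourth, the missing count will be reported, so a reader can recompute the other rate. That is true, but the count rests on the same undefined split between NE and missing. No hypothesis test or power calculation rests on ORR, and the primary endpoint is untouched.

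**Conclusion.** The concern holds. The ORR rule drops patients whom the plan's general rule keeps, no exception is stated, and the denominator cannot be fixed uniquely without definitions of the population and of NE versus missing. If the ORR rule is followed, the reported ORR is exactly 1/(1 − m) times the all-started rate.

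Whether that matters depends on m, which the documents do not give. At 1–2% it is negligible. At an assumed ORR of about 30% it exceeds sampling error only from about 11% missing for 678 patients and 21% for 163. Over assumed ORRs of 10% to 40% those thresholds run from 20% down to 9% and from 37% down to 17%. The conflict in the text is certain; the direction and size of any bias are not. The point should be fixed, but it concerns a secondary endpoint and leaves PFS, OS and TTD as they are.

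**What to change.** In section 9.7, ORR, replace the exclusion sentence and the formula together:

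- Main ORR = (CR + PR) / all patients who started the line, with missing BOR shown as its own category and kept in the denominator, as the general rule already requires.
- Beside it, as a sensitivity figure, (CR + PR) / (CR + PR + SD + PD + NE).
- Define the primary analysis population as all patients who started the line.
- Define NE and missing, and say where a patient who stopped or died before any response assessment belongs.

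Make the edit before the missing counts are seen, since choosing the denominator afterwards would be a data-dependent choice.

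The cost is a few lines of text and one extra table row, with no new data. The drawback is a somewhat lower headline ORR, which is conservative if some blanks are merely unrecorded responses (0.90 times the truth at m = 10% when unassessed patients respond as often as assessed ones). The second figure makes that visible.
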